## **Experiment 2. Optimization of visual stimulation for pain perception**

In this experiment we will optimize visual stimulation with the goal of reducing pain perception. To reduce the burden on participants, optimization has been designed as a two-step process, with the first step (implemented in Experiment 1) requiring no pain induction. Our preliminary hypothesis is that arousal-inducing visual stimuli will reduce the perception of acute pain, based on the well-known phenomenon of stress-induced analgesia (Vachon-Presseau et al., 2013; Yilmaz et al., 2010). Thus, once we optimize the stimuli to affect arousal state in Experiment 1, we will test the effectiveness of the optimized visual stimuli (OVS) in reducing pain perception and carry out additional adjustments to further increase their impact.

Location	Dandelions Science Laboratory 
Estimated number of participants	20 participants
Estimated experiment duration	2 hr

### ***Goals***

1. Find optimized visual stimuli
2. Determine optimization curve
3. Disentangle anxiety and pain responses

### ***Equipment and instruments***

1. Neurophysiological assessment: EEG, GSR, EMG, ECG
2. Behavioral assessment: VAS

3. Visual stimulation: DVN presented on a display
4. Infrastructure: 2 laptops / PCs for rendering & processing of the data
5. Nociception: Contact Heat Evoked Potentials (CHEPs)

### ***Conditions***

Up to three pain intensities levels (cold: 3°C, innocuous: 35°C, hot: 52°C) with OVS.

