## STUDY ENDPOINTS\*

Successful control of the arousal reduction of pain perception as measured by VAS and ERP for either thermal (CHEPs) or electric shock pain induction. While there is no single criterion for determining a clinically significant threshold, Dandelion Science has adopted the reported criterion of 20% reduction in pain intensity and expects to achieve a pain perception reduction of 20% on VAS scale for AI-guided visual stimulation as compared with no-visual-stimulation in response to at least one of the nociceptive conditions (CHEPs stimulation).

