### ***Experiment structure***

1. Measuring temperature and a short COVID symptom questionnaire
2. Signing of informed consent
3. Urine drug test
4. Signing of informed consent
5. Filling out the demographic questionnaire (5 minutes)
6. Filling out Perceived Stress Scale (Cohen, 1988)
7. Sensor setup (~30 minutes)
8. Sensor calibration (~5 minutes)
9. Instructions (~2 minutes)
10. Validating pain levels using step method
11. Training block (~2.5 minutes)
12. 12 Experimental blocks (~4 minutes per block; 8 stimuli). The blocks will be separated by breaks of 45 seconds.

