### ***Approximate trial structure***

1. Fixation cross 0.5 seconds
2. Stimulation 0.5 - 15.5 (15 seconds total)
3. Pain stimulation jitter window: 2 - 5 (pain stimulation of up to 800 ms can occur uniformly at any point within this window)
4. Behavioral response window: 15.5 to 30 seconds.

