#### ***Optimization training and testing\*:***

During the optimization procedure, we will use alpha and beta EEG bands, number of peaks in GSR, heart-rate variability and facial EMG spectrum, among other features, to guide the arousal and pain-control optimization procedure. The success of the optimized stimuli in reducing pain

perception will be evaluated using VAS. Prior data indicate that the minimal clinically relevant change in pain self-report should be 20%. In our study this effect will correspond to roughly an 8 mm change on the 100mm VAS. If the true difference in the mean response of matched pairs is 8 mm, we will need a sample of 30 participants to be able to reject the null hypothesis that the response difference is zero with a probability (power) of 0.8. The Type 1 error probability of this test is 0.05.

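### The VAS endpoint compares optimized visual stimulation with no visual stimulation, but Experiment 2 allocates no no-visual trials and no test phase with the stimulus frozen

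*Combined protocol and SAP*

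**What the plan says.** The Study Endpoints section expects a 20% VAS reduction "for AI-guided visual stimulation as compared with no-visual-stimulation in response to at least one of the nociceptive conditions". The section on optimization training and testing equates 20% with about 8 mm on the 100 mm VAS and bases the sample size on a paired analysis: "If the true difference in the mean response of matched pairs is 8 mm", 30 participants give power 0.8 at a Type 1 error of 0.05.

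Experiment 2 is where this would have to be measured. Its Conditions section reads "Up to three pain intensities levels (cold: 3°C, innocuous: 35°C, hot: 52°C) with OVS" and lists nothing else. The single trial template contains the step "Stimulation 0.5 - 15.5 (15 seconds total", entered separately from the pain stimulus. The Experiment structure and Block structure sections give 12 blocks of 8 trials, with no block or trial marked as a reference. The only pain stimulation described before those blocks is the step "Validating pain levels using step method".

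The introduction to Experiment 2 says the team will "test the effectiveness of the optimized visual stimuli (OVS) in reducing pain perception and carry out additional adjustments". No section says when adjustment stops or which trials count towards the endpoint.

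**The concern.** A paired OVS versus no-visual difference needs ratings from each participant under both conditions. The plan describes a source for only one of them.

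If the study runs as written, whoever analyses it must find a substitute comparator. The candidates are earlier OVS blocks or the pain-level validation. Both come before the trials they would be compared with, so any fall in ratings from habituation or time in session would look like a treatment effect. The validation step is also not described as a VAS baseline.

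A second, smaller problem is that OVS is tested while it is still being tuned. If the trials used to choose a stimulus also score it, the estimate can be biased by selection.

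**Working it through.** **Is there another source for the comparator?** Set side by side:

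- Experiment 1 uses the self-assessment manikin, and the opening Goals section says it involves no pain induction. Its control, random visual stimulation (RVS), is itself visual stimulation. Its cold pressor pilot monitors blood pressure and heart rate, not VAS.
- Experiment 2 lists VAS and CHEPs, with conditions under OVS only.
- The validation step and training block in Experiment 2 come before all OVS blocks, and neither is described as a no-visual VAS measurement.

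So no section supplies the no-visual ratings. Trial count: 12 blocks x 8 trials = 96 per participant, with 0 assigned to no visual stimulation and 0 to a fixed-stimulus test.

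**The plan's own sample size.** Inputs: 8 mm, power 0.8, alpha 0.05, n = 30. The SD of paired differences is not stated, so 30 cannot be reproduced independently; the SD has to be back-solved. For a two-sided paired t-test (sidedness assumed), the standardized difference giving 80% power at n = 30 is 0.529, so SD = 8 / 0.529 = 15.1 mm. The normal approximation gives 8 x sqrt(30) / (1.960 + 0.842) = 15.6 mm. The 15.1 mm figure is used below as a yardstick.

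**Drift (illustrative).** From block 1 to block 12 there are 11 steps. A drift of 8 / 11 = 0.73 mm per block would produce the whole target difference in a last-versus-first comparison. On the plan's figures, 8 mm is 20% of a mean of 8 / 0.20 = 40 mm.

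**Selection (illustrative).** As an upper case, suppose the best of 12 block means is picked directly on VAS, with 8 trials per block at one intensity and no real differences between blocks. The expected maximum of 12 standard normals is 1.629, so the bias is 1.629 x SD / sqrt(8). If selection is instead on a biomarker whose noise correlates r with VAS noise, multiply by r.

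| Assumed trial SD (mm) | Chosen on VAS | r = 0.5 | r = 0.3 |
|---|---|---|---|
| 10 | 5.8 mm | 2.9 mm | 1.7 mm |
| 15 | 8.6 mm | 4.3 mm | 2.6 mm |
| 20 | 11.5 mm | 5.8 mm | 3.5 mm |

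**Would a test phase inside the existing blocks be precise enough?** Take 4 blocks x 8 = 32 trials, 16 OVS and 16 no-visual, at one temperature. Trial noise in one participant's difference is SD x sqrt(2/16). With three temperatures analysed separately there are 32 / 6 = 5.33 trials per cell, and the noise is SD x sqrt(2/5.33). Shares are of the variance 15.1².

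| Assumed trial SD (mm) | One temperature | Share | Three, each separately | Share |
|---|---|---|---|---|
| 10 | 3.5 mm | 5.5% | 6.1 mm | 16.4% |
| 15 | 5.3 mm | 12.3% | 9.2 mm | 36.9% |
| 20 | 7.1 mm | 21.9% | 12.2 mm | 65.6% |

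**The case against.** The strongest reply is that omission is not exclusion. The trial structure is headed as approximate, the endpoint itself commits the study to a no-visual comparator, and the opening Goals section says Experiment 2 follows the general procedure of Experiment 1, which has a control. Control trials may be intended but unwritten. That is possible, but approximate timings do not supply a missing condition, the Conditions list is not labelled approximate, and the control carried over from Experiment 1 would be RVS, not a blank screen. It remains true that the loss occurs only if the written lists are what is run.

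The pairing is also an inference. The power statement does not name the members of the pair, and the endpoint does not say within participant. However, "AI-guided visual stimulation as compared with no-visual-stimulation" is the only pain comparator the plan states, and the two sections fit together only on that reading.

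The objections to the bias figures carry more weight. Every guiding feature the plan names is physiological, with VAS reserved for evaluation. The phrase "heart-rate variability and facial EMG spectrum, among other features" leaves room for VAS to guide tuning but does not say so. No section proposes scoring the best of 12 blocks or comparing late with early blocks. Averaging all OVS trials, including poorly tuned early ones, would tend to dilute an effect. With selection on biomarkers alone, the illustrated bias stays below 8 mm.

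Finally, no text is contradicted by the lack of a frozen test phase, and adaptive trials are the right data for the stated goal of tracing an optimization curve. They do not serve the VAS endpoint unless the plan says which trials enter it.

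**Conclusion.** The point holds and must be fixed before Experiment 2 data are collected. The endpoint and the power statement, read together, need a within-participant OVS versus no-visual difference. Experiment 2 allocates 0 of 96 trials to the no-visual side and defines no fixed-stimulus trials for the OVS side. This rests on the text alone, with the pairing inferred from those two sections.

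The drift and selection sizes show how large an artefact could be relative to 8 mm. They depend on assumed values, are not forecasts, and the conclusion does not need them. Confidence is high on the structural gap. The size of any selection bias is uncertain: it could exceed 8 mm only if VAS itself guided the choice of stimulus and trial noise were at the higher assumed values.

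**What to change.** - **Conditions (Experiment 2):** add a no-visual-stimulation condition (fixation only) at the same thermal conditions as OVS.
- **Introduction, Experiment structure and trial structure (Experiment 2):** within the existing 12 blocks, state a tuning phase followed by a test phase, for example the last 4 blocks. In the test phase freeze each participant's OVS and interleave OVS and no-visual trials in random order.
- **Endpoint:** base the VAS and N2/P2 comparison only on the paired OVS-minus-no-visual difference from test trials. Name in advance the thermal condition or conditions that enter it. Analysing three temperatures separately leaves about 5 trials per cell; pooling them equally over 16 and 16 trials would restore the one-temperature noise level.
- **Optional:** add RVS trials if an effect is to be credited to optimization rather than to watching any moving pattern. The stated endpoint does not need them.

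The cost is protocol wording and a stimulus-script change, with no added stimuli or session time. Tuning trials fall by one third, from 96 to 64 per participant, and further if control or RVS trials are also placed in tuning blocks. Whether 64 are enough is unknown: even for Experiment 1 the plan leaves the number of iterations open. The split between phases is therefore the sponsor's choice, provided it is fixed in advance.

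Two other discrepancies need separate reconciliation and are not solved here: 20 participants planned for Experiment 2 against 30 in the power statement, and the differing temperatures in the Conditions and CHEPs sections.

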### ***Experiment structure***

1. Measuring temperature and a short COVID symptom questionnaire
2. Signing of informed consent
3. Urine drug test
4. Signing of informed consent
5. Filling out the demographic questionnaire (5 minutes)
6. Filling out Perceived Stress Scale (Cohen, 1988)
7. Sensor setup (~30 minutes)
8. Sensor calibration (~5 minutes)
9. Instructions (~2 minutes)
10. Validating pain levels using step method
11. Training block (~2.5 minutes)
12. 12 Experimental blocks (~4 minutes per block; 8 stimuli). The blocks will be separated by breaks of 45 seconds.

### ***Approximate trial structure***

1. Fixation cross 0.5 seconds
2. Stimulation 0.5 - 15.5 (15 seconds total)
3. Pain stimulation jitter window: 2 - 5 (pain stimulation of up to 800 ms can occur uniformly at any point within this window)
4. Behavioral response window: 15.5 to 30 seconds.

### ***Block structure***

8 trials of 30 seconds = 4 minutes

### ***Data analysis***

#### *Optimization method*

To facilitate the search for effective visual stimulation we will use a Bayesian model, pretrained on the data collected in Experiment 1.

## Description of the procedures used in the study

**Nociceptive protocols:** Participants will be attached to the biosensors and seated in front of a digital display. Pain induction will be carried out as follows.

### 1. Cold pressor Test:

The cold pressor test is a simple and validated test in which the subject immerses one hand or foot into ice water for up to 3 min while blood pressure (BP) and heart rate are monitored. The cold stimulus activates afferent sensory pathways that, in turn, trigger a sympathetic response resulting in an increase in BP. The cold pressor test has been used in clinical and research settings to evaluate non-baroreflex-mediated sympathetic neural control in humans (Lamotte et al., 2021).

### 2. Contact Heat Evoked Potentials (CHEPs):

A contact heat stimulator will be employed to deliver stimulation (Pathway, Medoc, RamatYishai, Israel). The CHEPs thermode surface (diameter: 27 mm) consists of a heating thermo-foil covered with a layer of thermo-conductive plastic. The nominal heating rate of this device is 70 °C/ s, with a cooling rate of 40 °C/ s. The temperature of the thermode will be controlled through dedicated software, designed for optimization purposes. The thermode was attached to the participant's nondominant volar forearm. The stimulation will be conducted within the range of 40 °C for cold stimuli and 52 °C for hot stimuli. The duration of a single stimulation event will range from 800 ms to 10 seconds depending on the stimulation paradigm.

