#### ***EEG data preprocessing:***

Cleaning EEG data involves removing artifacts from the EEG signal. Although the EEG system is designed to record neural activity, it also records electrical activity arising from physiological entities such as eye blinking or jaw clenching. The EEG will be digitized continuously at a 512 Hz sampling rate. Data will be downsampled to 256 Hz and bandpass filtered using a 0.1 Hz high-pass cut-off (12db/octave) to reduce low-frequency noise such as drifting, and a 30 Hz low-pass cut-off (24db/octave) to reduce high-frequency noise such as muscle tension. Following this step, data will then be re-referenced to the average of all channels. Then a time-frequency analysis will be performed to extract temporal dynamics of the major EEG wave bands (alpha, beta, theta and gamma). Signal processing will be performed using the MNE toolbox (Gramfort et al., 2013) and performed in Python. In addition, the painful stimulation-onset ERPs will be computed and the areas of N2 and P2 components will be used for the analysis.

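### Experiment 2's cold level, 800 ms pulse limit and thermode ramp rates do not together describe one stimulus that the device can deliver

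*Combined protocol and SAP*

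**What the plan says.** Four places in the combined protocol and SAP bear on this.

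- **Experiment 2, Conditions**: "Up to three pain intensities levels (cold: 3°C, innocuous: 35°C, hot: 52°C) with OVS".
- **Experiment 2, Approximate trial structure**: "pain stimulation of up to 800 ms can occur uniformly at any point within this window". Here 800 ms is a maximum.
- **Description of the procedures, Contact Heat Evoked Potentials (CHEPs)**: the rates are given as "The nominal heating rate of this device is 70 °C/ s, with a cooling rate of 40 °C/ s". The same paragraph says "The stimulation will be conducted within the range of 40 °C for cold stimuli and 52 °C for hot stimuli", and "The duration of a single stimulation event will range from 800 ms to 10 seconds depending on the stimulation paradigm". Here 800 ms is a minimum.
- **Data Management, EEG data preprocessing**: "the painful stimulation-onset ERPs will be computed and the areas of N2 and P2 components will be used for the analysis".

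The documents do not give the temperature from which the thermode starts. They do not say whether 800 ms covers the ramps, the time at target or the whole excursion. They do not say whether ERP onset is the start of the ramp or the moment the target is reached.

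**The concern.** Two contradictions are visible on reading. Cold is 3 °C in one section and 40 °C in another, and 40 °C lies above the level the plan calls innocuous. The 800 ms figure is an upper bound in one section and a lower bound in another.

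A third problem appears only when the ramp rates are applied. A sponsor could correct the text so that 3 °C and 800 ms appear everywhere and still be left with a pulse that the device cannot complete in the stated time.

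Study Endpoints names VAS and ERP as the measures of pain reduction. If the stimulus is not defined, a result reported for the 3 °C level may not refer to the pulse that the protocol describes, and two operators could program different pulses from the same text. For the ERP, a window locked to the start of the ramp would cover different parts of the stimulus at the cold and hot levels.

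**Working it through.** **Nothing to reproduce.** The 800 ms limit is a design choice with no stated derivation, so there is no figure of the plan's own to recompute.

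**Inputs.** Cooling 40 °C/s and heating 70 °C/s (CHEPs section). Levels 3, 35 and 52 °C (Experiment 2, Conditions). Limit 0.8 s (Experiment 2, Approximate trial structure). The start temperature B is not stated. I take 35 °C, the innocuous level, as the main case and 32 °C as an alternative; a range of 20 to 40 °C is also shown. Ramps are treated as linear at the nominal rates.

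**Cold pulse to 3 °C and back, no hold.** Time down = (B − 3)/40; return = (B − 3)/70.

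| Start B | Down (s) | Return (s) | Total (s) |
|---|---|---|---|
| 20 °C | 0.425 | 0.243 | 0.668 |
| 25 °C | 0.550 | 0.314 | 0.864 |
| 30 °C | 0.675 | 0.386 | 1.061 |
| 32 °C | 0.725 | 0.414 | 1.139 |
| 35 °C | 0.800 | 0.457 | 1.257 |
| 40 °C | 0.925 | 0.529 | 1.454 |

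From 32 to 35 °C the full excursion exceeds 0.8 s by 42% (1.139/0.8) to 57% (1.257/0.8).

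**Hot pulse to 52 °C and back, no hold.** Time up = (52 − B)/70; return = (52 − B)/40.
- From 35 °C: 0.243 + 0.425 = 0.668 s, which fits.
- From 32 °C: 0.286 + 0.500 = 0.786 s, which fits.
- From 30 °C: 0.314 + 0.550 = 0.864 s, which does not fit.

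**Is there a start temperature that serves both?** The largest out-and-back excursion in 0.8 s is 0.8/(1/40 + 1/70) = 20.4 °C, in either direction.
- Cold needs B ≤ 3 + 20.4 = 23.4 °C.
- Hot needs B ≥ 52 − 20.4 = 31.6 °C.

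These ranges do not overlap.

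**What 800 ms might mean, from 35 °C.**
- Whole excursion: the cold pulse does not fit. The lowest temperature that allows a return in time is 35 − 20.4 = 14.6 °C.
- Ramp down and hold, return excluded: 3 °C is touched at exactly 0.800 s, with no hold. From 32 °C it is touched at 0.725 s, leaving 0.075 s.
- Time at target only: the excursion lasts 1.257 + 0.800 = 2.06 s. The plan does not say this is intended.

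**Time to target, cold against hot.**
- From 35 °C: 0.800 against 0.243 s, ratio 3.3.
- From 32 °C: 0.725 against 0.286 s, ratio 2.5.

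**The case against.** The best defence is that the result rests on premises the documents do not supply: a start temperature and a definition of 800 ms. The trial structure is headed as approximate, and the CHEPs section's own cold temperature, or its longer durations, would remove the infeasibility. This is fair, and it is why the point is a failure to reconcile rather than a proven impossibility. It does not clear the plan. The trial structure is the rule specific to Experiment 2, and only a pulse of exactly 800 ms satisfies both duration statements. Separate start temperatures for cold and hot would also resolve the overlap, but none are stated.

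A second defence is that the consequences are limited. The Conditions section allows up to three levels, so cold may not be used. Study Endpoints asks for success in at least one nociceptive condition, and the hot pulse fits from 32 or 35 °C. The main contrast is visual stimulation against none; made at the same thermal level, both sides share the same ramp. All of this stands and limits the point to the definition of the cold condition and to comparisons between levels.

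Four stronger conclusions might be drawn, and the documents support none of them:

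- **That 3 °C is never reached.** From 35 °C or below it is touched within 800 ms. What fails is holding it from 35 °C, or ending the pulse in time.
- **That the ERP is smeared.** A fixed ramp repeats on every trial and gives a constant delay, not trial-to-trial jitter. Loss of N2 or P2 area would need outside data.
- **That the cold ramp is always more than three times slower.** The rates differ by 70/40 = 1.75. The durations differ 3.3-fold from 35 °C but 2.5-fold from 32 °C. If the excursion is cut to fit 0.8 s, the ramp down takes 20.4/40 = 0.51 s, 2.1 times the hot ramp from 35 °C and 1.8 times from 32 °C.
- **That the cold level may not be painful.** Nothing in the documents establishes this, and Experiment 2 includes a step-method check of pain levels before testing.

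Nor does the plan say that ERPs will be pooled over temperatures; it is silent.

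**Conclusion.** The point holds as an internal inconsistency. The Experiment 2 conditions, its trial structure and the CHEPs description disagree on the cold temperature (3 against 40 °C) and on the role of 800 ms (maximum against minimum). The stated rates also do not allow a full excursion from 35 °C to 3 °C and back in 800 ms: it takes 1.26 s, or 1.14 s from an assumed 32 °C. If the limit includes the return, no single start temperature accommodates both the cold and the hot extreme. If it excludes the return, the cold target can be touched from 35 °C or below, with no hold at 35 °C.

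For the ERP, the supported conclusion is narrow. If onset means the start of the ramp, N2/P2 latencies are not directly comparable between cold and hot, because the target is reached at different times.

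The conclusion assumes linear ramps at the nominal rates. The size of the overrun depends on the start temperature, which the plan should state.

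**What to change.** Reconcile the cold level, the pulse duration and the device rates across Experiment 2's Conditions, its Approximate trial structure and the CHEPs section, so that each listed condition is one the thermode can deliver. State the start temperature, for each level if it differs, and say whether 800 ms includes the ramps. Which temperature or duration is right is for the investigators; none is proposed here.

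In EEG data preprocessing, define ERP time zero against the recorded thermode temperature, and state that N2/P2 areas are compared within temperature level.

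The cost is a few lines of protocol text and one analysis sentence. The thermode temperature trace must be recorded and aligned with the EEG. The cold condition may have to be described differently from an 800 ms pulse at 3 °C.
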